### 8.3.9 Modified Nail Psoriasis Severity Index (mNAPSI) score

Psoriatic nail disease will be evaluated at the Baseline visit using the mNAPSI. All affected nails will be scored (0 to 3) for onycholysis/oil drop dyschromia, nail plate crumbling, and pitting and will be scored (0 for “no” or 1 for “yes”) for leukonychia, nail bed hyperkeratosis, splinter

haemorrhages and red spots in the lunula. The score for an individual nail ranges from 0 to 13 with higher scores indicative of more severe nail disease. The total mNAPSI score is the sum of the scores for each individual nail. If a nail is unaffected, it will be recorded as such and will not contribute to the total mNAPSI score.

If any of the 7 response items that contribute to mNAPSI is present, while other items are missing (ie, partial mNAPSI data), then the missing items are assumed to be 0 for the mNAPSI calculation. In some cases, the data may be captured in such a way that only non-zero component scores are present in the database. Again, those components that are not present are simply assumed to be 0 for the mNAPSI calculation.

Change from Baseline in mNAPSI score for subjects with nail PSO at Baseline is defined as Post-Baseline mNAPSI score minus Baseline mNAPSI.

An mNAPSI75 responder is defined as a subject who achieved at least a 75% improvement from Baseline in the mNAPSI score. mNAPSI90 and mNAPSI100 are defined accordingly. The proportion of mNAPSI75/90/100 responders for subjects with nail PSO at Baseline over time will be summarized for each study period (Initial randomized, Maintenance) by treatment group and OLE by treatment sequence.

### **8.3.10 Psoriatic Arthritis Screening and Evaluation (PASE)**

The PASE questionnaire is a self-administered tool to screen for active PsA in subjects with PSO (Husni et al, 2014). The questionnaire consists of 15 items that are divided into a 7-item symptoms subscale and an 8-item functions subscale. Standardized responses are based on 5 categories relating to agreement (strongly agree [5], agree [4], no idea [3], disagree [2], and strongly disagree [1]). The total maximum score is 75 points (symptom score: 35 points and function score: 40 points). Psoriatic Arthritis Screening and Evaluation questionnaire scores  $\geq 47$  points are indicative of active PsA.

PASE will be collected at Baseline, Week 48/PEOT, Week 96 and Week 144/PEOT visits. PASE will be summarized based on OC only. No imputation is applied.

- Change from Baseline in the PASE questionnaire scores (function score, symptom score, and total score) is defined as Post-Baseline PASE questionnaire score (function, symptom, and total) minus Baseline PASE questionnaire score (function, symptom, and total).
- Shift from Baseline in PASE score suggestive of PsA ( $< 47$  versus  $\geq 47$ ) is defined to Week 48/PEOT visit time point relative to Baseline.

Change from Baseline in the PASE and Shift from Baseline in PASE will be summarized for each study period (Initial randomized, Maintenance) by treatment group and for OLE by treatment sequence and visit.

### **8.3.11 Euro-Quality of Life 5-Dimensions, 3 levels (EQ-5D-3L)**

The EQ-5D-3L health questionnaire provides a descriptive profile and a single index value for health status. The instrument is comprised of a 5-item health status measure and a VAS measurement.

Responses to EQ-5D-3L are scored as 1 for “no problem”, 2 for “some or moderate problems”, and 3 for “extreme problems”.

Absolute EQ-5D-3L VAS score records the respondent's self-rated health status on a vertical 20cm scale, 0 to 100 graduated (0=worst imaginable health status, 100=best imaginable health status).

Change from Baseline in EQ-5D-3L VAS scores is defined as Post-Baseline EQ-5D-3L VAS score minus Baseline EQ-5D-3L VAS score.

Responses to EQ-5D-3L will be summarized for each study period (Initial randomized, Maintenance) by treatment group and for OLE by treatment sequence and visit. The analysis will be based on OC only as primary analysis. No imputation is applied to responses to EQ-5D-3L but is applied to EQ-5D-3L VAS scores.

### **8.3.12 Work Productivity and Activity Impairment Questionnaire – Specific Health Problem (WPAI-SHP)**

The WPAI-SHP is a subject-reported questionnaire that assesses subject's employment status, work absenteeism, work impairment while working, overall work, and daily activity impairment attributable to a specific health problem. Five out of 6 items of the WPAI-SHP are regrouped into the 4 dimensions, with scores expressed as percentage, where higher numbers indicate greater impairment and less productivity, i.e., worse outcomes, as described in the WPAI-SHP scoring rules.

The scoring rules for the WPAI-SHP are as follows:

Questions:

- 1 = currently employed
- 2 = hours missed due to specified problem
- 3 = hours missed other reasons
- 4 = hours actually worked
- 5 = degree problem affected productivity while working
- 6 = degree problem affected regular activities

Scores:

- Percent work time missed due to problem:  $[Q2 \text{ hours}/(Q2 \text{ hours} + Q4 \text{ hours})]*100$
- Percent impairment while working due to problem:  $[Q5 \text{ score}/10]*100$
- Percent overall work impairment due to problem:  
 $[Q2 \text{ hours}/(Q2 \text{ hours} + Q4 \text{ hours}) + [(1 - (Q2 \text{ hours}/(Q2 \text{ hours} + Q4 \text{ hours})) \times (Q5 \text{ score}/10)] ] *100$
- Percent activity impairment due to problem:  $[Q6 \text{ score}/10]*100$

Change from Baseline score is derived as post Baseline score minus Baseline score. A negative change score indicates a reduction in the score/improvement for the subject.

The Change from Baseline in WPAI-SHP will be summarized for each study period (Initial randomized, Maintenance) by treatment group and for OLE by treatment sequence at each visit.

## 8.4 Additional Statistical Analysis of other Efficacy Variables

For selected other efficacy variables, it is of interest to perform statistical tests and to calculate inferential statistics. As these tests are not part of the multiplicity-controlled procedure, the associated p-values are considered nominal and are not controlled for multiplicity. For responder variables, the analysis will follow what was specified for the primary analysis. Specifically, a stratified Cochran-Mantel-Haenszel (CMH) test will be used, where region and prior biologic exposure (yes/no) will be stratification variables. The p-value will be based on the CMH test for a general association. Missing values will be imputed using NRI. For continuous variables, the MI – MCMC / Monotone Regression approach used for other continuous variables will be applied for the imputation model. The analysis model will be based on analysis of covariance (ANCOVA) with fixed effects of treatment, region, and prior biologic exposure and Baseline value as a covariate. Below is a list of variables for which these nominal p-values will be calculated (with the time points in parentheses). The results of these inferential tests will all be presented in a single table summarizing the testing performed outside of the multiplicity-controlled testing procedure.

- PASI90
  - Bimekizumab vs Secukinumab (Weeks 1, 2, 4, 8, 12, 16 and 48)
- IGA Clear or Almost Clear
  - Bimekizumab vs Secukinumab (Weeks 1, 2, 4, 8, 12, 16 and 48)
- PASI100
  - Bimekizumab vs Secukinumab (Weeks 4, 8, and 12)
- IGA Clear
  - Bimekizumab vs Secukinumab (Weeks 4, 8, 12, 16, and 48)
- PASI75
  - Bimekizumab vs Secukinumab (Weeks 1, 2, and 16)
- Scalp IGA Clear or Almost Clear (subjects with Baseline Scalp IGA  $\geq 2$ )
  - Bimekizumab vs Secukinumab (Weeks 16 and 48)
- pp-IGA Clear or Almost Clear (subjects with Baseline pp-IGA  $\geq 2$ )
  - Bimekizumab vs Secukinumab (Weeks 16 and 48)
- mNAPSI75 response (subjects with Baseline mNAPSI > 0)
  - Bimekizumab vs Secukinumab (Weeks 16 and 48)
- mNAPSI90 response (subjects with Baseline mNAPSI > 0)
  - Bimekizumab vs Secukinumab (Weeks 16 and 48)
- mNAPSI100 response (subjects with Baseline mNAPSI > 0)
  - Bimekizumab vs Secukinumab (Weeks 16 and 48)

- DLQI 0/1 response
  - Bimekizumab vs Secukinumab (Weeks 16 and 48)
- PASI percentage change from Baseline
  - Bimekizumab vs Secukinumab (Weeks 1, 2, 4, 8, 12, 16, and 48)
- PASI  $\leq 1$  response
  - Bimekizumab vs Placebo (Weeks 1, 2, 4, 8, 12, 16, and 48)
- PASI  $\leq 2$  response
  - Bimekizumab vs Placebo (Weeks 1, 2, 4, 8, 12, 16, and 48)
- PASI  $\leq 3$  response
  - Bimekizumab vs Placebo (Weeks 1, 2, 4, 8, 12, 16, and 48)
- PASI  $\leq 5$  response
  - Bimekizumab vs Placebo (Weeks 1, 2, 4, 8, 12, 16, and 48)
- Patient Symptom Diary responses for itch, pain, and scaling
  - Bimekizumab vs Secukinumab (Weeks 16, 32, 48)

## 9 PHARMACOKINETICS AND PHARMACODYNAMICS

For the Week 48 interim the following treatment groups were summarized for the Initial and Maintenance Treatment Period.

- Bimekizumab 320mg Q4W/Q8W with switch from Q4W to Q8W occurring at Week 16
- Bimekizumab 320mg Q4W.

PK and ADAb will also be summarized through to Week 144 by the following treatment sequence and by visit for Initial, Maintenance, and Open-Label Extension treatment period combined. No PK or ADAb samples will be collected in the OLE2 treatment period.

- Subjects receiving bimekizumab in the double-blind treatment period until Week 144 or until treatment discontinuation:
  - Bimekizumab 320mg Q4W/Q8W with switch from Q4W to Q8W occurring at Week 16
  - Bimekizumab 320mg Q4W/Q8W with switch from Q4W to Q8W occurring at Week 48
  - Bimekizumab 320mg Q4W/Q8W with switch from Q4W to Q8W occurring at Week 72 or 84
  - Bimekizumab 320mg Q4W/Q8W with switch from Q4W to Q8W occurring at Week 96 or later
  - Bimekizumab Total (only for immunogenicity analyses).

Subjects with any other treatment sequence groups (eg, Bimekizumab 320mg Q4W/Q8W/Q4W or Q4W/Q8W/Q4W/Q8W) will be allocated the "Bimekizumab Total" treatment sequence group for immunogenicity analysis only. All data will be included in the listings.

- Subjects receiving secukinumab in the double-blind treatment period:
  - Bimekizumab 320mg Q8W from Week 48
  - Bimekizumab 320mg Q4W/Q8W with switch from Q4W to Q8W occurring at Week 72 or 84
  - Bimekizumab 320mg Q4W/Q8W with switch from Q4W to Q8W occurring at Week 96 or later
  - Bimekizumab Total (only for immunogenicity analyses)

Note that subjects who received Bimekizumab 320mg Q4W only, ie, those who discontinued before switching to Q8W, will be allocated to the corresponding Q4W/Q8W treatment sequence group depending on when the subject discontinued. For example, if a subject discontinued at week 68, they will be allocated to group Bimekizumab 320mg Q4W/Q8W, switch occurring at Week 72 for PK summary table and figure purposes.

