### 2.3.2.3 Maintenance Treatment Period

At Week 16 subjects in the bimekizumab 320mg treatment arm will be re-randomized 1:2 to receive bimekizumab 320mg Q4W or bimekizumab 320mg Q8W. To maintain the blind after re-randomization, subjects in the bimekizumab 320mg Q8W treatment arm will receive placebo at Weeks 20, 28, 36, and 44. Subjects in the secukinumab arm will continue to receive secukinumab 300mg Q4W.

Subjects will be classified as completing the maintenance treatment period if they complete the Week 48 Visit without early withdrawal from the study or if they start treatment in the Open-Label period. The start of the Open-Label extension period marks the end of the maintenance treatment period for subjects opting to participate in the OLE period. Otherwise the end of the maintenance period is marked by the Week 48 visit.

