### 2.3.2.4 OLE Period

After completion of the Week 48 visit assessments, subjects will be allowed to enroll in the OLE Period. All subjects enrolling in the OLE Period will sign a new ICF, and then receive the following IMP regimens as determined by the subject's treatment regimen and PASI response in the double-blind Treatment Period.

At Week 48, subjects receiving:

- Bimekizumab 320mg Q4W who achieve PASI90 at Week 48 of the double-blind Treatment Period will be randomized 1:1 to receive bimekizumab 320mg Q4W or bimekizumab 320mg Q8W.
- Bimekizumab 320mg Q4W who do not achieve PASI90 at Week 48 of the double-blind Treatment Period will receive bimekizumab 320mg Q4W.
- Bimekizumab 320mg Q8W who achieve PASI90 at Week 48 of the double-blind Treatment Period will receive bimekizumab 320mg Q8W.
- Bimekizumab 320mg Q8W who do not achieve PASI90 at Week 48 of the double-blind Treatment Period will receive bimekizumab 320mg Q4W.

- Secukinumab who achieve PASI90 at Week 48 of the double-blind Treatment Period will be randomized 1:1 to receive bimekizumab 320mg Q4W or bimekizumab 320mg Q8W.
- Secukinumab who do not achieve PASI90 at Week 48 of the double-blind Treatment Period will receive bimekizumab 320mg Q4W.

From Week 64 the subjects who are receiving bimekizumab 320mg Q4W at the time of implementation of protocol amendment 5.0 will have their dosing interval changed to bimekizumab 320mg Q8W at the next clinical site assessment as described on [Table 7–2](#) for subjects who are receiving bimekizumab 320mg Q4W and have reached Week 96 prior to the implementation of Protocol Amendment 5.0, if PASI90 is achieved, the subject's dosing interval will change from 320mg Q4W to 320mg Q8W (default), unless, based on medical judgment, the Investigator decides differently. Otherwise, if PASI90 is not achieved they will have their dosing interval changed to bimekizumab 320mg Q8W at the next clinical site assessment after implementation of protocol amendment 5.0 as detailed above.

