## **2.4 Determination of sample size**

A total of 700 subjects will be randomly assigned in a 1:1 ratio at Baseline to one of the following treatment groups:

- Bimekizumab 320mg (350 subjects)
- Secukinumab 300mg (350 subjects).

The primary efficacy analysis is based on the comparison of bimekizumab to secukinumab for the primary efficacy variable of PASI100 response at Week 16. The assumed responder rates for PASI100 at Week 16 are 60% and 44% for bimekizumab and secukinumab, respectively. The assumed responder rate for bimekizumab is based on the Phase 2b PS0010 data. The assumptions related to the responder rates for secukinumab are based on those observed in the CLEAR study (Thaçi et al, 2015). The power to show statistical superiority of bimekizumab relative to secukinumab under these assumptions is 98% for the primary endpoint. The power for the non-inferiority comparison (with 10% non-inferiority margin) under these assumptions is >99%.

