## 9.1 Pharmacokinetics

Pharmacokinetic variables will be analyzed for all subjects in the PK-PPS. Bimekizumab plasma concentrations will be summarized for each treatment sequence as described in Section 9, at each scheduled visit. A separate summary table will be created for the Open-Label Extension Period for subjects that are both in the PK-PPS and the OLS.

PK summaries will be based on observed values. No imputation will be used however, if plasma concentration measurements are below the level of quantification (BLQ), then for calculation of the derived statistics the result will be set to 0.125 µg/ml, which is ½ of the lower level of quantification (LLOQ). Descriptive statistics including geometric mean, geometric coefficient of variation, and geometric mean 95% CI if applicable will be calculated if at least 2/3 of the values of interest are above the LLOQ. If this is not the case, only median, minimum, and maximum will be presented. In cases where  $n < 3$  only the minimum and maximum will be presented.

In addition, geometric mean plasma concentration (with the 95% CI) will be plotted versus time on linear and semi-logarithmic scales by treatment sequence group. The summary table and figures will be repeated by cumulative antibody status for subjects randomized to bimekizumab.

If a dose is +/- 21 days out of window, then the plasma concentration from that visit and all subsequent visits will be excluded from the PK summary tables and graphs.

If the PK sampling date is >1 day after the dosing date, the plasma concentration at this visit will be excluded from the PK summary tables and figures, but not from the listing.

If a subject misses an administration of bimekizumab, receives less or more than the intended dose, then the plasma concentration from the next scheduled visit will be excluded from PK summary tables and graphs.

All PK concentration data will be listed.

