#### Analysis

- Immunogenicity will be assessed through summary tables, figures, and listing of individual results by subject. The analysis of immunogenicity will be summarized by treatment sequence as described in Section 9 and visit. All analyses will be run on the safety population, unless specified otherwise. Summary of anti-bimekizumab antibody status overall and by each visit separated by treatment sequence
- Summary of the time-point of the first occurrence of anti-bimekizumab antibody positivity during the treatment period by treatment sequence. A plot of the titer by time to first anti-bimekizumab antibody positivity will be prepared
- All individual subject-level anti-bimekizumab antibody results will be listed.
- The number and percentage of subjects in each of the 8 anti-bimekizumab antibody categories during the treatment period by treatment sequence, with an additional category combining subjects in categories 2 and 5, summarized as total treatment emergent. In addition, the count and percentage of subjects who are pre anti-bimekizumab positive will be calculated (this is the sum of categories 3, 4, and 5)
- The prevalence of immunogenicity, separated by treatment sequence, and defined subcategory, will be reported by visit, defined as (cumulative) proportion of subjects having confirmed positive anti-bimekizumab antibody samples at any visit up to and including that visit. Missing samples will not be included in the denominator
- The time to achieving treatment-emergent anti-bimekizumab antibody positivity, separated by treatment sequence and defined sub-category, will be analyzed based on Kaplan-Meier methods. Subjects will be considered to have an event at the time point at which treatment emergent anti-bimekizumab antibody positive is first achieved. Subjects classified as treatment-emergent anti-bimekizumab antibody negative will be censored at the time of the last available anti-bimekizumab antibody result

- A summary of PASI 100 responders, separated by treatment sequence and defined sub-category, at weeks 16, 48 and 144 as a function of ADA b titer will be presented graphically. This will be repeated for PASI 75 and 90 responders

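### In the concentration tables and figures through Week 144, Q8W subjects who miss PASI90 at Week 48 and enter the OLE have no column at any visit, so membership at early visits depends on a later outcome

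*SAP*

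**What the plan says.** SAP Section 9 fixes one grouping for all visits, with the double-blind and OLE periods taken together: "PK and ADA b will also be summarized through to Week 144 by the following treatment sequence and by visit for Initial, Maintenance, and Open-Label". For subjects who started on bimekizumab, the groups are set by when the change from Q4W to Q8W occurred: Week 16, Week 48, Week 72 or 84, or Week 96 or later. A Bimekizumab Total group is added for immunogenicity only. Any other sequence is covered by one sentence: "Subjects with any other treatment sequence groups (eg, Bimekizumab 320mg Q4W/Q8W/Q4W or Q4W/Q8W/Q4W/Q8W) will be allocated the" Total group, again for immunogenicity only, with all data kept in the listings.

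Section 9.1 states "Pharmacokinetic variables will be analyzed for all subjects in the PK-PPS" and then applies the Section 9 sequences to concentrations at each scheduled visit.

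Which sequence a subject ends up with depends on Section 2.3.2.4. One rule is "Bimekizumab 320mg Q8W who do not achieve PASI90 at Week 48 of the double-blind Treatment Period will receive bimekizumab 320mg Q4W". Its counterpart is "Bimekizumab 320mg Q8W who achieve PASI90 at Week 48 of the double-blind Treatment Period will receive bimekizumab 320mg Q8W".

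The antibody analyses in Section 9.3.2 use the same sequences, including "A summary of PASI 100 responders, separated by treatment sequence and defined sub-category, at weeks 16, 48 and 144" plotted against antibody titer.

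For the Week 48 interim, Section 9 describes two different groups, defined only by the regimen after Week 16.

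**The concern.** A column in a by-visit table should be defined by what was known at or before that visit. Here the column for Weeks 1 to 48 is settled by the PASI result at Week 48 and the dose interval that follows from it. Two subjects re-randomised to Q8W at Week 16 have the same assigned regimen up to Week 48. If one misses PASI90 at Week 48 and continues into the OLE, that subject's concentrations leave the table from the first visit onwards.

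The omission is one-sided. Q8W non-responders who continue are dropped, while Q4W non-responders who continue stay on Q4W and are tabulated in a later-switch group. Section 2.1.3 lists pharmacokinetics, immunogenicity and maintenance of efficacy on Q4W versus Q8W among the study's objectives. The filtered displays include the concentration tables and figures repeated by antibody status, so they leave out some of the subjects in whom a link between exposure, antibodies and failure would be looked for.

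**Working it through.** The plan states no figure on this point, so there is none to reproduce. The check maps the Week 48 rules onto the Section 9 groups and then makes a head count under stated assumptions.

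**Mapping (Section 2.3.2.4 against Section 9), bimekizumab subjects entering the OLE**

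| Regimen from Week 16 | PASI90 at Week 48 | First OLE regimen | Concentration column through Week 144 |
|---|---|---|---|
| Q8W | yes | Q8W | Week 16 switch |
| Q8W | no | Q4W (later Q8W under Amendment 5.0) | none |
| Q4W | yes, randomised to Q8W | Q8W | Week 48 switch |
| Q4W | yes, randomised to Q4W | Q4W, later Q8W | Week 72/84 or Week 96 or later |
| Q4W | no | Q4W, later Q8W | Week 72/84 or Week 96 or later |

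The second row gives Q4W/Q8W/Q4W or Q4W/Q8W/Q4W/Q8W, the two examples named in Section 9. Among OLE entrants, the Week 16 switch group is therefore 100% PASI90 responders at Week 48 by rule. OLE entry is optional (Section 2.3.2), and Q8W subjects who do not enter stay in the Week 16 switch group whatever their response.

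**Head count**

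Inputs from the SAP: "Bimekizumab 320mg (350 subjects" planned (Section 2.4), who at Week 16 "will be re-randomized 1:2 to receive bimekizumab 320mg Q4W or bimekizumab 320mg Q8W" (Section 2.3.2.3). Planned on Q8W before any loss: 350 × 2/3 = 233.

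Assumptions, because the SAP gives no rates:
- loss before Week 16, a = 2% to 5%
- no OLE entry after re-randomisation, b = 5% to 15%
- PASI90 at Week 48 among Q8W OLE entrants, r = 75% to 95%

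Formulas:
- Q8W subjects: N = 350 × (1 − a) × 2/3
- removed: N × (1 − b) × (1 − r)
- kept responders: N × (1 − b) × r
- kept non-entrants: N × b

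Results:
- N: 350 × 0.98 × 2/3 = 229; 350 × 0.95 × 2/3 = 222.
- Most removed: 229 × 0.95 × 0.25 = 54, or 54/229 = 24%.
- Fewest removed: 222 × 0.85 × 0.05 = 9, or 9/222 = 4%.
- Middle case (a = 2%, b = 10%, r = 85%): 229 × 0.90 × 0.15 = 31 removed; 175 responders and 23 non-entrants kept.

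Share of Week 48 responders at double-blind visits, counting non-entrants as non-responders: 175/(175 + 23) = 88% in the middle case, against 175/229 = 76% in the whole Q8W arm. Across the assumed ranges this is 81% to 95% against 64% to 90%. If subjects who stopped before Week 16 are also placed in the Week 16 switch group, under the note on Q4W-only subjects, the share is 74% to 92%.

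**The case against.** The strongest reply is that the unselected summary already exists. Section 9 says the Week 48 interim grouped concentrations by regimen after Week 16, and the sequences through Week 144 come in addition. This stands: a reader might infer that these subjects disappear from all concentration summaries, and they do not. The omission concerns the through-Week-144 tables and figures. The separate OLE concentration table in Section 9.1 names no other grouping, so it does not clearly bring them back.

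A reader might also conclude that the titer plots cannot show loss of response on Q8W. That goes too far. The subjects stay in Bimekizumab Total for antibodies, and non-entrants stay in the Week 16 switch group. PASI90 at Week 48 also does not fix PASI100 at Week 48, or any response at Weeks 16 or 144. Section 4.8 separately summarises PASI response by antibody positivity on the Randomized Set. What is lost is the sequence column.

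Nor do the documents support saying that Q8W exposure is made to look as good as Q4W. These are descriptive summaries, no exposure difference between responders and non-responders is given, and OLE entrants in the Week 48 switch group are likewise all responders.

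Finally, the sentence on all PK-PPS subjects is not strictly contradicted, because the next sentence defers to Section 9, which states the exception openly. Placing subjects who stopped on Q4W by time of stopping is an explicit rule with a worked example; a separate group for them would be largely a matter of presentation.

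**Conclusion.** The point holds for the concentration tables and figures through Week 144. Q8W subjects who miss PASI90 at Week 48 and enter the OLE have no column at any visit, including double-blind visits at which they shared an assigned regimen with the tabulated Week 16 switch group. Among OLE entrants that group is all Week 48 responders by rule; at double-blind visits it is mostly, not wholly, responders. In the by-sequence antibody outputs the same subjects lose their column but remain in Total.

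The mechanism follows from the SAP alone. The size does not: 9 to 54 subjects (4% to 24%) rests entirely on the assumed loss, OLE entry and response rates. The direction of any bias in exposure is not established, and no primary or secondary efficacy test is touched. This is a worthwhile, low-cost correction to descriptive outputs.

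**What to change.** - Add a Q4W/Q8W/Q4W(/Q8W) column to the through-Week-144 concentration tables and figures, and to the by-sequence antibody and PASI-by-titer outputs. Section 3.6 already gives Q4W/Q8W/Q4W its own row for key OLE efficacy variables, labelled as Week 48 non-responders.
- In those same outputs, group visits up to Week 48 by the regimen assigned at Week 16, as the Week 48 interim did. Use the switch-time groups only for visits after Week 48.

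The cost is SAP wording and an extra column. No new data are needed and no dosing rule is affected. The downside is that the added group is small, so at some visits it may support only limited statistics.
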